5 POPULATION

5.1 Number of Subjects

Approximately 340 males and females, 6 months of age and older, with a minimum of 3 and a maximum of 70 lesions of MC at baseline will be randomized in a 2:1 (active:vehicle) scheme.

5.2 Inclusion Criteria

1. Be 6 months of age or older, and in good general health;
2. Have a written informed consent form signed by subject or a parent or legal guardian and an assent form as required;
3. Have between 3 and 70 treatable MC at Baseline;
4. Female subjects age 9 and above must have a negative UPT at Baseline;
5. Female subjects age 9 and above must agree to practice a medically acceptable form of birth control during the study and for 30 days after their final study visit;
6. Be willing and able to follow study instructions and likely to complete all study requirements.

5.3 Exclusion Criteria

1. Have strongly suggested sexually transmitted MC and do not agree to refrain from sexual activities throughout the study period.
2. Are immunosuppressed, have immunodeficiency disorder, or are on immunosuppressive treatment;
3. Have significant injury on and/or surrounding MC that may impact ability to treat and count lesions;
4. Have received treatment with topical calcineurin inhibitors or steroids on MC or within 2 cm of MC lesions within 14 days prior to Baseline;
5. Have received treatment for MC during the 14 days prior to Baseline with podophyllotoxin, imiquimod, cantharidin, sinecatechins, topical retinoids, oral or topical zinc, or other homeopathic or over the counter (OTC) products including, but

- not limited to, ZymaDerm and tea tree oil, cimetidine and other histamine H2 receptor antagonists (including Zantac);
6. Have received surgical procedures related to MC (cryotherapy, curettage, other) within 14 days prior to Baseline;
 7. Have MC only in periocular area;
 8. Female subjects who are pregnant, planning a pregnancy or breastfeeding;
 9. Have known hypersensitivity to any ingredients of SB206 or Vehicle Gel including excipients;
 10. Have participated in a previous study with a berdazimer sodium product (SB204, SB206, SB208, SB414);
 11. Have more than 1 family member currently participating in a study with a berdazimer sodium product (SB204, SB206, SB208, SB414)
 12. Have participated in any other trial of an interventional investigational drug or device within 14 days or concurrent participation in another interventional research study.
 13. History or presence of clinically significant medical, psychiatric, or emotional condition that, in opinion of the investigator, would compromise the safety of the subject or the quality of the data.

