1 INTRODUCTION AND RATIONALE

1.1 Background

Molluscum contagiosum (MC) is a common skin disorder that affects mainly healthy children ([Dohil et al, 2006](#)). MC has the greatest incidence in individuals aged 1–14 years ([Schofield et al, 2011](#)); prevalence in children is between 5% and 11% ([Olsen et al, 2014](#)).

MC virus is an important human skin pathogen and can cause disfigurement and suffering in children. In adults MC is less common and often sexually transmitted. Extensive and persistent skin infection with the virus can indicate underlying immunodeficiency. MC virus is distinct from other poxviruses because of its host and tissue adaptations. It infects only the skin and, rarely, the mucous membranes. The virus has developed efficient mechanisms to grow in differentiating cells of the human epidermis and is well adapted to human hosts ([Chen et al, 2013](#)).

Extensive and persistent skin infection with the virus can indicate underlying immunodeficiency. Patients with atopic dermatitis (AD) have an impaired skin barrier in addition to immunological changes which could explain the rising prevalence and high number of lesions in this population. Topical corticosteroids and calcineurin inhibitors (both local immunosuppressants commonly applied to the skin in patients with atopic dermatitis) have been implicated as contributing factors in some patients ([Osio et al, 2011](#)).

MC is transmitted between human hosts by the infectious matter discharged from the lesions. According to a prospective community cohort study ([Olsen et al, 2015](#)), the mean time to resolution was 13.3 months (SD 8.2). Eighty (30%) of 269 cases had not resolved by 18 months; 36 (13%) had not resolved by 24 months. Transmission to other children in the household occur in 102 (41%) of 250 cases in the literature.

Novan has conducted Study NI-MC201, a phase 2, multi-center, double-blind, vehicle-controlled ascending dose, 12-week study to assess the tolerability, safety, and efficacy of SB206 in subjects with molluscum contagiosum. In this study, the safety and efficacy of SB206 was evaluated in 256 subjects, males or females, 2 years of age or older, with 3 to 70 MC lesions. Different concentrations and dosing frequency of SB206 was tested for up to 12 weeks and the number of the subjects of each dose group were: 47 (4% BID), 48 (8% BID), 47 (12% BID), 48 (12% QD) and 66 (Vehicle).

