4 STUDY PLAN

4.1 Study Design

This is a Phase 3 multi-center, randomized, double-blind, vehicle-controlled, parallel group study to be conducted in approximately 340 subjects with MC. After obtaining informed consent/assent, subjects who satisfy entry criteria will be randomized 2:1 (active:vehicle). Subjects receiving current treatment for MC at the time of the Screening Visit will enter a wash out period of up to 14 days prior to randomization. In the event no wash out period is required. Screening and Baseline visit activities may be combined into a single visit. At randomization, subjects will be stratified into four strata corresponding to the cross-classification of household number of randomized subjects (1 subject per household vs 2 subjects per household) and investigator type (dermatologist vs other). Households randomizing 2 subjects will receive the same treatment assignment for both subjects. Up to two subjects from the same household may be randomized on the same day, if both individually meet all inclusion/exclusion criteria. For subjects in the same household, Screening can occur on different days; however, the Baseline visit must occur on the same day.

Subjects or their caregivers will apply SB206 12% or Vehicle Gel once daily for a minimum of 4 weeks and up to 12 weeks to all lesions identified at Baseline and new treatable lesions that arise during the course of the study. Subjects or their caregivers will continue to treat the area until the next scheduled visit even if the lesion(s) clear. If the investigator determines all lesions are cleared at a clinic visit, the treatment may stop. At Weeks 2, 4, and 8, the investigator will count and record the number of active (raised, treatable) molluscum lesions per body area. The investigator will also determine if new lesions have occurred since the last visit, and the subject or caregiver will be instructed by the investigator to re-initiate treatment. If treatment is stopped due to clearance, subjects will continue regularly scheduled visits through Week 24.

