If a subject's treatment is discontinued by the investigator or the subject because of an AE, that AE should be indicated as the reason for treatment discontinuation. All subjects will be encouraged to remain in the study throughout the 24-week study duration.

In the event of suspected allergic contact dermatitis, photographs may be taken of the affected area(s) and transmitted to the CRO medical monitor for review prior to initiating patch testing.

When approximately 200 subjects (cumulative across studies NI-MC302 and NI-MC302) have completed 4 weeks of treatment, a Data Safety Monitoring Board (DSMB) will review all available unblinded safety data (including completed patch testing results).

Table 1: Schedule of Assessments

	Screening	Treatment					
	Screening ¹ (Day -14 to Day 1)	Visit 1 ¹ Baseline (Day 1)	V2 Telephone Contact (Day 2)	Visit 3 ² Week 2 (Day 15 ±3)	Visit 4 ² Week 4 (Day 29 ±5)	Visit 5 ² Week 8 (Day 57 ±5)	Visit 6 ² Week 12/ ET1 (Day 85 ±5)
Informed Consent (Assent)	X						
Demographics	X						
Medical and Medication History	X						
Lesion Count or Recurrence	X	X		X	X	X	X
Physical Exam		X					X
Urine Pregnancy Test ³	X	X			X	X	X
BOTE Inflammation Score ⁴		X (pre-dose)		X	X	X	X
Local Skin Reactions (LSR) (post-dose) ⁴		X		X	X	X	X
Scarring/Keloid Assessment					X	X	X
DLQI/CDLQI ⁵		X					X
Review of Inclusion/Exclusion Criteria	X	X					
Drug Dispensed		X			X	X	
Dispense Subject Diary		X		X	X	X	
Review Subject Application Instructions		X		X	X	X	
In Clinic Study Drug Application ⁶		X		X	X	X	X
Review Study Drug Compliance				X	X	X	X
Collect Study Drug					X	X	X
Collect Subject Diary				X	X	X	X
Record Adverse Event (AE) and Concomitant Medication (CM) Changes ⁷		X	X	X	X	X	X

	Safety Follow-up		
	Visit 7 ² Week 16 Telephone Contact (Day 113±5)	Visit 8 ² Week 20 Telephone Contact (Day 141±5)	Visit 9 ² Week 24/ ET2 (Day 169±5)
Scarring/Keloid Assessment			X
Record Adverse Event (AE) and Concomitant Medication (CM) Changes ⁷	X	X	X

¹Screening and Baseline may occur on the same day. If this occurs, lesion count and review of inclusion/exclusion criteria will only occur once. If two members of the same household qualify for study participation, they must be randomized on the same day.

²All visit dates are in reference to Baseline, e.g. Week 2 occurs 14 days after Baseline Visit.

³Females 9 years of age and older.

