9.5 Protocol Deviations

Significant protocol deviations that could potentially affect the efficacy or safety conclusions of the study will be identified prior to database lock and unblinding of individual subject treatment information. Significant protocol deviations may include, but are not limited to:

- Randomly assigned subjects who did not satisfy selected inclusion and exclusion criteria
- Randomly assigned subjects who developed withdrawal criteria during the study but were not withdrawn
- Subjects who were randomized incorrectly including subjects of the same household who are randomized to different treatments
- Subjects who received the wrong treatment
- Subjects where the subject/site staff were unproperly unblinded
- Week 12 Lesion Count not performed
- Subjects who received an excluded concomitant treatment.

The decision on the criteria for whether a subject is excluded from the PP Population will be made during the data review meeting prior to unblinding and database lock. Reasons for exclusion of a subject from the analysis will be listed.

A listing of all protocol deviations including the deviation designation (major or minor and significant or not), category, and indication of whether the deviation led to an exclusion of a subject from the PP Population will be presented in a data listing.

Major and significant protocol deviations will be summarized by deviation category and treatment group.

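### Exclusion criterion 11 admits a child whose sibling is in MC302, so one home can hold two treatment assignments

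*Combined protocol and SAP*

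**What the plan says.** **Eligibility.** Criterion 11 in protocol Section 5.3, repeated in the synopsis, excludes subjects who "Have more than 1 family member currently participating in a study with a berdazimer sodium product (SB204, SB206, SB208, SB414"). Two or more relatives in such studies exclude a subject; one does not. Criterion 10 concerns the subject's own earlier berdazimer studies. Criterion 12 concerns the subject's own other trials: "Have participated in any other trial of an interventional investigational drug or device within 14 days or concurrent participation in another interventional research study".

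**Household rules.** Section 4.1 states that "Households randomizing 2 subjects will receive the same treatment assignment for both subjects", and Section 8.3 says the same. Section 4.1 also states "Up to two subjects from the same household may be randomized on the same day, if both individually meet all inclusion/exclusion criteria", and for members of one household "Screening can occur on different days; however, the Baseline visit must occur on the same day". Table 1 footnote 1 adds: "If two members of the same household qualify for study participation, they must be randomized on the same day". Section 4 of the SAP repeats the same-day Baseline rule.

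**If it goes wrong.** SAP Section 9.5 gives, as an example of a significant deviation, "Subjects who were randomized incorrectly including subjects of the same household who are randomized to different treatments".

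**Sister study.** Protocol Section 13.2 and SAP Section 10.5 count subjects cumulatively across MC301 and MC302 for the DSMB safety review. The MC302 protocol is not among the documents.

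**The concern.** The sponsor clearly wants one assignment per home. Subjects or caregivers mix and apply the gel at home. Two gels under different assignments in one home create two risks: one child's gel may be used on the other, and the family may guess the assignments by comparing the gels or the skin reactions. The first shrinks the treatment contrast; the second weakens the blind.

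Criterion 11 is the only eligibility criterion about relatives in berdazimer studies. It refers to any such study, so it foresees a relative in another trial and allows one. It also says family member, whereas stratification, assignment and the GEE cluster all use household. These are different sets of people: a cousin living elsewhere is family but not household, and an unrelated child in the same home is the reverse.

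**Working it through.** **1. Which routes to two assignments in one home are open?**

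| Route | Criterion 11 | Other control in this trial's documents | Status |
|---|---|---|---|
| Two siblings enter this trial on the same day | Passes | Same assignment for both (4.1, 8.3) | Closed |
| A sibling enters this trial on a later day | Passes | Same-day Baseline (4.1; SAP Section 4) and same-day randomization (Table 1 footnote 1) | Barred, but not by a listed criterion |
| One sibling here, one in MC302 | Passes | None found: criteria 10 and 12 address the subject only, and the same-day and same-assignment rules are not extended to another study | Open |

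The questions asked about the household (Section 6.2.1; Table 1 footnote 7) concern who has MC, not who is in a trial.

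**2. Chance of different arms.** This trial allocates 2:1 (Section 8.3). The MC302 ratio is not given.
- MC302 at 2:1 (assumed), independent: 2 × (2/3) × (1/3) = 0.444, or 44%.
- MC302 at 1:1 (assumed): (2/3)(1/2) + (1/3)(1/2) = 0.50, or 50%.

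**3. The plan's power figures.** Inputs from Section 11.2: 113 vehicle, 227 active, two-sided alpha 0.05. With p_v and p_a the vehicle and active rates:

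power = Φ[(p_a − p_v − 1.960 × SE0) / SE1], where SE0 uses the pooled rate and SE1 the separate rates.

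For 18% against 36%: pooled rate = (113 × 0.18 + 227 × 0.36)/340 = 0.3002; SE0 = 0.05277; SE1 = 0.04818; z = (0.18 − 0.1034)/0.04818 = 1.589; power = 94.4% (plan: 94%). The other two scenarios give 93.4% (plan: 93%) and 82.8% (plan: 83%). All three reproduce.

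**4. Illustration of cross-use.** Suppose a share x of vehicle subjects responds at the active rate. The vehicle rate becomes 0.18 + 0.18x, with the active rate held at 0.36. Only this direction is counted.

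| x (assumed) | Vehicle rate | Difference | z | Power |
|---|---|---|---|---|
| 0 | 18.00% | 18.00 points | 1.589 | 94.4% |
| 2% | 18.36% | 17.64 points | 1.506 | 93.4% |
| 5% | 18.90% | 17.10 points | 1.382 | 91.6% |
| 10% | 19.80% | 16.20 points | 1.179 | 88.1% |

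**5. What those shares require.** With MC302 at 2:1, a vehicle subject's MC302 sibling is on active with probability 2/3. Even if every such vehicle subject received the full active effect, x = 2%, 5% or 10% would need 3%, 7.5% or 15% of vehicle subjects to have a sibling in MC302 (x ÷ 2/3). The documents give no figure for this share.

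**The case against.** The best defence is that criterion 11 is not meant to work alone. It allows one relative because the design allows two subjects per household, and the same-day and same-assignment rules do the rest. A requirement need not be an eligibility criterion to bind. For breaches there is the deviation list in SAP Section 9.5, and SAP Section 11.1 plans a one-subject-per-household analysis and allows one for mis-stratification. All of this stands for pairs within this trial. It does not reach a pair split between the two studies. The deviation route also acts only afterwards, through the Per-Protocol set, while the primary analysis is ITT.

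MC302's own eligibility rules, sites and IWRS are not available either. The gap is therefore shown for this trial's text only; MC302 may have a safeguard of its own.

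A reader might infer three stronger things that the documents do not support:
- **That a sibling infected later can join this trial under another assignment.** Section 4.1, Table 1 footnote 1 and SAP Section 4 rule this out.
- **That the household stratum, covariate and GEE cluster become wrong.** On the MC302 route this trial holds one randomized subject from that home, so the one-subject stratum and a cluster of one are correct for its analysis.
- **That such siblings will be common.** Section 1.1 reports that "Transmission to other children in the household occur in 102 (41%) of 250 cases in the literature", but it attaches no time window, and the same paragraph gives a mean time to resolution of 13.3 months. This is not a rate over recruitment or 12 weeks, and a sibling must also qualify for and join MC302.

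**Conclusion.** The point holds for the cross-study route. This trial's eligibility rules admit a child with a sibling in MC302, and nothing in its documents keeps the two on the same treatment. Within this trial the rule of one treatment per household is protected; what remains there is a matter of placement and wording, since the same-day rule is outside Section 5.3 and family member does not match household.

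The consequence is some risk of cross-use and unblinding, not a modelling error. Its size is unknown and probably small: in the illustration, power stays at 88.1% or more up to a 10% share of vehicle subjects responding at the active rate. That rests on assumed shares and on full transfer of the active effect; the 44% discordance rests on an assumed 2:1 ratio in MC302. The change is worth making because it is cheap, not because the primary result is in evident danger.

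**What to change.** Reword criterion 11 in Section 5.3 and the synopsis along these lines: *Have a household member who is currently participating in another berdazimer sodium study or was randomized in this study on an earlier day, or have more than one other household member being randomized in this study.* Have the IWRS ask this at randomization.

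This keeps same-day pairs, puts the same-day rule where sites confirm eligibility, closes entry to this trial from an MC302 household, and uses household throughout. It cannot stop a sibling of a child already in this trial from joining MC302 later; that needs a matching criterion in the MC302 protocol, which should be checked.

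The cost is one eligibility sentence, one IWRS question and a few siblings who become ineligible. The planned analyses and the sample size do not change.

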5.4 Subject Screening

Written informed consent (assent form where required) will be obtained before any study-related procedures are performed. The investigator may discuss the study and the possibility for entry with a potential subject without first obtaining consent. A subject wishing to participate must give written informed consent/assent prior to any study-related procedures being conducted, including those performed solely for the purpose of determining eligibility for study participation or withdrawal from current medication (if required prior to study entry). The investigator has both the ethical and legal responsibility to ensure that each subject being considered for inclusion in this study has been given a full explanation of the procedures and expectations for study participation.

The site-specific informed consent forms (ICF)/assent forms must be forwarded to the contract research organization (CRO) for approval prior to submission to an Institutional Review Board (IRB) and/or Independent Ethics Committee (IEC) as appropriate. Each subject will sign the ICF that has been approved by the same IRB responsible for protocol approval. Each ICF/assent form

must adhere to the ethical principles stated in the Declaration of Helsinki and will include the elements required by Food and Drug Administration (FDA) regulations in 21 CFR as well as the International Conference on Harmonisation (ICH) Good Clinical Practice (GCP) guidelines, and applicable federal and local regulatory requirements. The ICF/assent form(s) must also include a statement that Novan and the CRO (or their designees) and auditing regulatory agencies will have direct access to the subject's records and medical history.

Once the appropriate essential information has been provided to the subject/caregiver and fully explained by the investigator (or a qualified designee) and it is felt that the subject/caregiver understands the implications and risks of participating in the study, the IRB approved ICF/assent document shall be signed and dated by both the subject/caregiver and the person obtaining consent (investigator or designee), and by any other parties required by the IRB or other regulatory authorities. The subject/caregiver will be given a copy of the signed ICF/assent document with the original kept on file by the investigator. All of the above activities must be completed before any study related procedures are conducted.

5.4.1 *Screening Failures*

A subject is considered screened once they have a signed ICF/assent and completed one screening assessment. A screen failure subject will be any screened subject who does not get randomized to a treatment arm. Subjects will be allowed to rescreen once.

5.5 *Deviation from Inclusion/Exclusion Criteria*

Deviation from the Inclusion/Exclusion Criteria is not allowed. Any deviation identified during the study should be discussed with the CRO and/or Novan.

6 STUDY CONDUCT

6.1 *General Instructions*

Prospective subjects as defined by the eligibility criteria (Inclusion/Exclusion Criteria) will be considered for entry into this study. Subjects' ICF/assent must be obtained prior to conducting any procedures. Some Baseline procedures (i.e., review of inclusion/exclusion criteria, brief physical exam, adverse event assessment, concomitant medication review, and UPT) must be completed prior to randomization. Subjects who meet all eligibility criteria who do not require washout from any current treatment may be screened and randomized on the same day.

After the required procedures are completed and study eligibility is confirmed, the subject will be randomized to treatment utilizing an Interactive Web Response System (IWRS) which will identify the study drug to be dispensed to the subject. The subject/caregiver will be trained on the

mixing, application, and storage of the study drug. The first application should be done at the clinic, and application should also be done in clinic at Week 2, Week 4, Week 8, and Week 12.

6.2 Study Procedures by Time Point

6.2.1 Screening (Day-14 to Day 1)

The following procedures must be performed and recorded at the Screening visit:

1. Review study procedures and information regarding the study including the potential risk and benefits of SB206 with the subject/caregiver and obtain written ICF/assent.
2. Obtain demographic information.
3. Obtain subject's medical history (including start date of the subject's current episode of molluscum (i.e., when molluscum was first noticed by the subject/caregiver)), household MC status, medication history, and concomitant medication information.
4. Perform lesion mapping and lesion count.
5. If applicable, obtain UPT and evaluate results. If pregnancy test is positive, the subject may not participate in the study.
6. Review inclusion/exclusion to confirm whether subject qualifies to participate in the study.

